## 1.4 Correlative/Exploratory Studies

### 1.4.1 SABR induced immune response

Previous studies have demonstrated multiple immunogenic properties of radiation therapy (RT), especially when given at high doses such as with SABR [57, 58]. Since SABR is a highly focused therapy, it does not inherently immunocompromise the host. In addition, as opposed to conventional radiation fields, SABR is a highly focused therapy that spares the surrounding lymph nodes which are vital for an effective immune response. By not surgically removing the tumor, the body retains the antigen depot (dying tumor cells) within the host. Furthermore, since SABR causes local inflammation, dendritic cells (DCs) are attracted into the tumor. The antigen-presenting properties and the induction of immunogenic cell death by SABR are well documented [59]. SABR-induced tumor cell death is primarily via mitotic catastrophe or necrosis, both of which are known to be immunogenic cell deaths as opposed to apoptosis, which is immunologically tolerogenic [60]. *In vivo* studies have shown that radiation induces release of damage (or danger)-associated molecular patterns (DAMPs) such as HMGB1, HSP and calreticulin into the extracellular matrix and thereby promotes the recruitment and activation of antigen-presenting cells (APCs) such as DCs for antigen presentation [61-63]. Subsequently, the APCs migrate to the draining lymph nodes for the presentation of the antigens and efficiently present tumor antigens in the cell surface MHC molecules to T cells [64]. The T cells initiate an adaptive immune response resulting in antibody production and the expansion of cytotoxic T cells. These are delivered to both the primary and metastatic tumor sites. Increased trafficking of CD8+ T cells to both irradiated tumor and their draining lymph node has been demonstrated [64, 65]. Furthermore, RT causes a dose-dependent increase in MHC I tumor neo-antigen presentation by the tumor cells [66]. This, in conjunction with a demonstrated increase in FAS death receptors on the tumor cell surface in response to radiation, renders tumor cells particularly susceptible to CD8+ T cell-mediated cytotoxic attack [67, 68].

The correlative studies will explore the mechanisms of possible immune enhancement by SABR. Activation of each arm of the immune response will be evaluated separately utilizing different assays. The humoral response will be evaluated using ELISA to measure the titer of tumor-specific antibodies generated by SABR against tumor tissue collected from the respective patients and established human renal cancer cell line Caki-2 (clear cell) and ACHIN (adenocarcinoma). An overall increase in tumor antigen-specific antibody will be measured using immunoblotting with patient sera as a source of primary antibody.

Enhancements of increased cytotoxicity to renal cancer cells can be measured by cytotoxicity assays. Antibody-dependent cell-mediated cytotoxicity (ADCC) measures the cell-killing ability of certain lymphocytes that require the target cell to be marked by an antibody and thus measures the humeral response [69]. On the other hand, lymphocyte-mediated cytotoxicity assay will measure the formation of tumor-specific CTLs among the lymphocytes collected from patients with the controls being lymphocytes collected from the same patients before SABR. Since it is not practical or feasible to obtain sufficient quantities of tumor cells from each patients to assess a quantitative cytotoxicity by these assays, established allogenic human renal cancer cell line Caki-2 and ACHIN will be used for this purpose. It is a generally accepted principle of tumor immunology that there will be many common tumor antigens between different patient tumors of same site origin, and therefore tumor cell lines as well [69]. In fact, the tumor antigens (PSA, CEA, CA 19-9 etc.) that are in clinical practice are reported to be present in a significant portions

of patients of the respective tumor site. This concept of commonality of tumor antigens between allogenic tumor cell lines and patients is put into clinical practice by the GVAX anti-tumor vaccine which is currently in early phase clinical trials for pancreatic, melanoma and renal cancer [70, 71]. GVAX consists of multiple human tumor cell lines of the respective site, that is modified to express GM-CSF, and killed with radiation prior to injection in patients. The presence of common tumor antigens in the cell lines and patient's tumors, leads to induction of an immune response. The LNCaP and PC-3 cell lines has been shown to express many of the common renal cancer antigens, and therefore, is an appropriate surrogate to be used instead of patient's own cells and has been used in similar *in vitro* cytotoxicity assays [72-76].

Cytokines are hormonal messengers responsible for most of the effects in the immune system such as activation of innate versus adaptive immune response, cellular versus humoral immune response [77, 78]. For example, an increased level of IL-2 and IFN- $\gamma$  suggests activation of Th1 cells leading to activation of macrophages and suggests a cell-mediated adaptive immune response whereas IL-4 and IL-5 may indicate Th2 activation and induction of humoral immunity [69, 78]. An increase in IL-17 may suggest activation of autoimmune responses [79]. Therefore, measurements of serum cytokine levels have generally been used previously in clinical trials as surrogates to assess specific activation of immune pathways [80, 81]. Serum cytokines from this clinical trial before and after SABR will be measured using an extensive array of cytokines to explore the specific immune pathways that are initiated by SABR. The planned array of cytokines will measure levels of the following cytokines before and after treatment for each patients: Th1/Th2/Th17 cytokines: IFN- $\gamma$ , IL-1 $\beta$ , IL-2, IL-4, IL-5, IL-8, IL-10, IL-12p70, IL-13, IL-17 TNF- $\alpha$ ; pro-inflammatory cytokines: GM-CSF, IFN- $\gamma$ , IL-1 $\beta$ , IL-2, IL-6, IL-8, IL-10, IL-12p70, TNF- $\alpha$ ; Chemokines: Eotaxin, MIP-1 $\beta$ , TARC, IP-10, IL-8, MCP-1, MCP-4, KC, and others including IL-6, IL-12, TGF- $\beta$  and HMGB1.

Many surrogate markers for activated and proliferating lymphocytes have been described. Some of these markers include CD25, CD71, CD45RO, CD107a, CD54, CD69, Ki67 and ICOS/CD278 [82-85]. These markers are easily measured with antibodies specific for the markers that are tagged with a fluorophore utilizing FACS analysis. Also using FACS, activation markers on other immune cells such as CD80 and CD 86 on DCs, and inhibitory markers on monocytes such as PD-1 can be measured as surrogates of immune activation or inhibition. These measurements from PBMCs collected from patients before and after treatment will give us further information regarding the intensity of the immune response. Additionally, PD-L1, the ligand of PD-1, often expressed in tumor cells, can be quantified from patient pre-treatment tumor biopsy.

The relative levels of different monocyte subpopulations in the tumor biopsy sample after treatment as well as in the peripheral circulation often dictate the overall outcome of an immune response, and has been reported in previous immunotherapy trials [86]. Exploration of possible mechanisms of treatment failure can be explored from this analysis as well. Therefore, different subpopulation of monocytes and lymphocytes will be quantified in patient PBMCs (and in tumor biopsy samples where applicable) collected before and after treatment utilizing markers specific for those cells.

Many studies have suggested that imaging characteristics of tumor may be used to predict treatment outcome of radiation therapy for various tumors, such as lung [87], prostate[88], cervical[89]. By analyzing CT and MRI images on patient enrolled in this trial, we plan to explore whether image characteristics of CT and MRI acquired prior to the SBAR treatment, such as intensity features, texture features and geometry features, are correlated with the treatment outcome of SABR for RCC. Through analysis of the change of these image characteristics in the follow-up scans, we will also explore whether the change of these features can be used for early prediction of SABR treatment response.

Multiple clinical and pre-clinical studies have demonstrated the dependence of tumor radiation resistance with tumor hypoxia, including those performed in our institution [90-94]. Using a combination of blood oxygen level dependent (BOLD) and tissue Oxygen Level Dependent

(TOLD) MRI, accurate insight regarding tumor oxygenation can be obtained. In RCC, tumor hypoxia and its dependence on treatment outcome, specifically with SABR, has not been explored before. Therefore, BOLD and TOLD MRI sequences will be incorporated in the baseline and six month post-treatment scans for patients enrolled in this trial.

#### **1.4.2 Tumor respiratory motion modeling**

Respiratory motion causes significant geometric and dosimetric errors in the administration of stereotactic radiotherapy (SBRT) for renal cell cancer (RCC). The purpose of this study is to create and validate patient-specific motion models of the abdominal anatomy with high spatial and temporal resolution. These models will be used to develop novel four-dimensional (4D=3D+time) techniques for radiotherapy treatment planning and real-time motion-adaptive dose delivery.

This study will involve the acquisition of real-time optical surface monitoring data from human patients with primary lesions, following their 4D computed tomography scan (4DCT - standard-of-care at our clinic). These data will be used to build a 4D motion model that describes the spatial location of each voxel in the CT volume as a function of time. In the treatment room, before dose delivery, the model will be updated and validated using three 15s long kV fluoroscopic sequences, each acquired from a different angle, and time-correlated with optical surface monitoring. The data and the findings of this study will be used solely for research and will not affect a patient's clinical treatment plan or dose delivery. The data acquired in this study will vastly improve our knowledge of how respiratory motion affects tumors and organs at risk within the abdominal anatomy and enable the development of better motion-managed radiation therapy paradigms that may help other patients with thoracic and abdominal cancers.

## **2.0 STUDY OBJECTIVES**

### **2.1 Primary Objective**

- 2.1.1 To evaluate if SABR to SRMs is able to eliminate its growth and viable tumor.

### **2.2 Secondary Objectives**

- 2.2.1 To describe the adverse events associated with the administration of SABR to SRMs
- 2.2.2 To measure the growth rate of SRMs after SABR treatment.
- 2.2.3 To measure the changes in kidney function, creatinine levels, renal perfusion and GFR after SABR treatment.
- 2.2.4 To measure tumor viability pathologically one year after SABR treatment with a biopsy.
- 2.2.5 To assess radiographic changes of the SRM after SABR treatment, including tumor viability, %enhancement, necrosis, T2 signal, tumor cellularity with diffusion-weighted imaging
- 2.2.6 To assess local, regional and systemic progression of disease after SABR to SRM
- 2.2.7 To assess time to progression (TTP) of disease from the first SABR treatment.

- 2.2.8 To assess progression free survival (PFS). PFS is defined as the length of time from start of treatment to the time of loco-regional disease progression (as defined in Section 2.4) or death from any cause.
- 2.2.9 To assess overall survival (OS). OS is defined as the duration of time from start of treatment to the time of death from any cause.
- 2.2.10 To assess tumor growth, local failure and indeterminate disease response (IDR) as defined in section 6.1.4

## **2.3 Exploratory Objectives**

- 2.3.1 To evaluate the cytokine changes brought on by SABR to SRM and to evaluate generation of any immune response specific to tumor cells.
- 2.3.2 To evaluate whether radiographic spatial-temporal tumor features extracted from CT and MRI can be used to predict treatment response of tumor to SABR.
- 2.3.3 To evaluate if tumor oxygenation as measured by BOLD/TOLD MRI sequences is able to predict tumor response to SABR.
- 2.3.4 To model kidney and tumor motion with respect to respiration

## **2.4 Endpoints**

### **2.4.1 Primary Endpoint:**

Local control of the SRMs will be defined as <4mm increase in the longest tumor diameter compared to pre-treatment scan on an MRI or contrast-enhanced CT scan in the setting of no radiographic or pathologic evidence of viable tumor.

### **2.4.2 Secondary Endpoints:**

- 2.4.2.1 Adverse Events: Acute and late adverse events will be assessed using NCI's CTCAE v4.0 toxicity criteria and RTOG/EORTC criteria (Appendix A and B).
- 2.4.2.2 Growth Rate: Growth of the longest diameter of the SRMs after SABR treatment will be compared to baseline and expressed as growth rate of cm/year.
- 2.4.2.3 Loco-regional and systemic progression: Loco-regional and systemic progressive disease will be defined based on local, regional and systemic progression as defined by AJCC (7th edition) kidney cancer staging and any stage >T1a (>4cm) constitutes a progression.
- 2.4.2.4 Kidney function: To assess kidney function creatinine levels and renal perfusion scan will be performed at baseline and periodically after SABR (See section 5).
- 2.4.2.5 Radiographic changes: Radiographic changes of the SRM after SABR treatment will be assessed using MRI interpretation by a radiologist.
- 2.4.2.6 Tumor Growth, Local failure and Indeterminate Disease Response as defined in section 6.1.4

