Based on the published retrospective and the two prospective phase I trials, the dose fractionations evaluated in this trial is 8Gy x 5, 10Gy x 4 and 12 Gy x 3. In a retrospective study published paper by Wersäll, et al, from the Karolinska Hospital, 50 patients with kidney cancer, both primary and metastatic, were retrospectively analyzed [50]. High rates of local control were achieved with doses ranging from 25 Gy to 45 Gy. The most common doses used were 40 Gy in 5 fractions and 45 Gy in 3 fractions. Another retrospective study used the dose of 40Gy in 5 fractions and both studies reported excellent control rate [45]. Therefore 8Gy x 5 is evaluated in this study. The 4 and 3 fraction equivalent doses to this dose levels are 10Gy and 12 Gy respectively, which are the two other dose levels included in this trial. Justification of the three fraction dose equivalent of 12Gy x 3 comes from the phase I study that did not see any failures at this level.

The study population for this trial is patients with biopsy proven primary RCC that are candidates for active surveillance (AS). Keeping patient safety in perspective, it is reasonable to offer an experimental treatment such as this to a patient population that would have otherwise been put in AS. At any sign of progression, the patients that have undergone SABR in this trial will be offered the standard of care (SOC) of radical nephrectomy, partial nephrectomy or ablation as deemed appropriate by the treating urologist—which is same as what would have been offered to them had they been in AS. The AUA defines AS patients to be those with small renal mass (SRM) with <3cm tumors. The NCCN recommends AS for patients with T1a tumors or tumors <4 cm. A number of retrospective and one prospective study reported on the natural history of SRMs [51-55]. A meta-analysis reviewed multiple retrospective studies and reported an average growth rate of 0.28 cm/year for these tumors [51]. They further reported a growth of 0.4 cm/year in the subset of patients that had biopsy confirmed RCC. Keeping clinical application in perspective, it is logical to use SABR only to tumors that are growing, since one third of the SRMs do not grow. Therefore, patients

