3.1.2 Renal mass  $\leq$  5cm

3.1.2.1 The treating renal mass must be  $\leq$  5cm. Other renal masses (cysts etc.) of any size will not make the subject ineligible.

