## 5.5 Removal of Subjects from Study

Subjects can be taken off the study treatment and/or study at any time at their own request, or they may be withdrawn at the discretion of the investigator for safety, behavioral or administrative reasons. The reason(s) for discontinuation will be documented and may include:

- 5.5.1 Subject voluntarily withdraws from treatment (follow-up permitted);
- 5.5.2 Subject withdraws consent (termination of treatment and follow-up);
- 5.5.3 Subject is unable to comply with protocol requirements;
- 5.5.4 Subject demonstrates disease progression (follow-up permitted)
  - 5.5.4.1 Tumor size >4cm
  - 5.5.4.2 Loco-regional progression as defined in AJCC 7; stage >T1a.
- 5.5.5 Subject experiences toxicity that makes continuation with the remaining SABR fractions unsafe;
- 5.5.6 Treating physician judges continuation on the study would not be in the subject's best interest;
- 5.5.7 Subject becomes pregnant (pregnancy to be reported along same timelines as a serious adverse event) prior to the completion of SABR treatments;
- 5.5.8 Subject becomes unable to undergo imaging studies after enrollment, subject will be either replaced or withdrawn from study based on investigator's assessment;
- 5.5.8 Development of second malignancy (except for basal cell carcinoma or squamous cell carcinoma of the skin) that requires systemic treatment which could interfere with this study;
- 5.5.9 Lost to follow-up. If a research subject cannot be located to document survival after a period of 2 years, the subject may be considered "lost to follow-up." All attempts to contact the subject during the two years must be documented and approved by the Data Monitoring Committee.

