#### **6.1.4 Response Criteria**

##### **6.1.4.1 Evaluation of Lesions**

Complete Response (CR): Disappearance of all target lesions. Disappearance of all target lesions. Any pathological lymph nodes (whether target or non-target) must have reduction in short axis to <10 mm (the sum may not be "0" if there are target nodes). Determined by two separate observations conducted not less than 4 weeks apart. There can be no appearance of new lesions.

Partial Response (PR): At least a 30% decrease in the sum of the longest diameter (LD) of target lesions, taking as reference the baseline sum LD. There can be no appearance of new lesions.

Progressive Disease (PD): > 20% increase in the SLD taking as reference the smallest SLD recorded since the treatment started (nadir) and minimum 5 mm increase over the nadir.

Stable Disease (SD): Neither sufficient shrinkage to qualify for PR nor sufficient increase to qualify for PD, taking as reference the smallest sum LD since the treatment started. There can be no unequivocal new lesions.

Tumor Growth (TG): At least a 4mm increase in the LD of treated lesion in a single scan when compared to baseline scan (or an increase of >2.0mm in two consecutive scans).

Local Control: No TG AND a complete radiographic or pathologic absence of tumor viability.

Local Failure: Any TG OR any radiographic or pathologic evidence of tumor viability.

Indeterminate Disease Response: (IDR): 1) Presence of radiographic evidence of viable disease without any increase in the LD (<4mm) sufficient enough to qualify for TG; 2) complete absence of radiographic evidence of viable disease regardless of any change in tumor diameter.

A biopsy is recommended in the case of tumors with ≥4mm increase in size with no radiographic evidence of viable tumor, OR any tumors with radiographic evidence of viable tissue.

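### Tumours above 4 cm and up to 5 cm are eligible but already meet the protocol's progression definition, so they become PFS events without growing

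*Protocol*

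**What the plan says.** **Entry.** Section 3.1.2.1: "The treating renal mass must be $\leq$ 5cm". There is no lower limit and no separate rule for masses above 4 cm.

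**Progression as an endpoint.** Section 2.4.2.3 defines loco-regional and systemic progression by AJCC staging and adds that "any stage >T1a (>4cm) constitutes a progression". The protocol itself thus equates a stage above T1a with a size above 4 cm.

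**Progression as a reason for removal.** Section 5.5.4 names disease progression and gives two forms of it: "Tumor size >4cm" (5.5.4.1) and "Loco-regional progression as defined in AJCC 7; stage >T1a" (5.5.4.2).

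**Where the definition is used.** Section 2.2.8 defines PFS from start of treatment to loco-regional progression as defined in section 2.4, or death. Section 2.2.7 (TTP) names no definition. Section 9.3 estimates both by Kaplan-Meier.

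**Other size rules.** The primary endpoint (2.4.1) requires less than 4 mm of increase from the pre-treatment scan and no evidence of viable tumour. Section 6.1.4.1 defines tumour growth on a single scan as at least 4 mm over baseline, and progressive disease as "> 20% increase in the SLD taking as reference the smallest SLD recorded since the treatment started (nadir"), with an increase of at least 5 mm over that nadir.

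**The concern.** Progression should record a change after treatment starts. Sections 2.4.2.3 and 5.5.4.1 instead record a state: the tumour is above a fixed size. Because the entry limit is 1 cm higher than that size, some eligible patients are in that state before the first fraction.

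In a 16-patient trial each such patient moves the PFS curve by 6.25 points (1/16), for a reason that has nothing to do with SABR. A tumour that shrinks from 4.5 to 4.1 cm still meets the definition, while one that doubles from 2.0 to 4.0 cm does not.

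Conduct is also touched. Section 4.12 says subjects will be removed from therapy when a section 5.5 criterion applies. The note in section 5.3 moves subjects with progressive disease to survival-only follow-up. Read literally, both apply to an eligible 4.5 cm tumour from the outset, and the second could cost the imaging and biopsy needed for the one-year primary endpoint.

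**Working it through.** The plan gives no figure to reproduce here. The check sets the passages against each other and then sizes the effect.

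**Inputs.** Entry limit 5 cm (3.1.2); progression limit above 4 cm (2.4.2.3, 5.5.4.1); N = 16 (9.2); tumour growth at 4 mm over baseline, and RECIST progressive disease at more than 20% and at least 5 mm over nadir (6.1.4.1). The share of patients entered above 4 cm is not stated, so a range is assumed.

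**1. Distance to the progression limit.** Growth needed to exceed 4 cm = 4.0 cm minus entry size.

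| Entry size | Growth needed to exceed 4 cm | Tumour growth (single scan) reached at | RECIST PD reached above (nadir = entry size) |
|---|---|---|---|
| 3.9 cm | just over 1 mm | 4.3 cm | 4.68 cm |
| 4.1 cm | none (1 mm above already) | 4.5 cm | 4.92 cm |
| 4.5 cm | none (5 mm above already) | 4.9 cm | 5.40 cm |
| 5.0 cm | none (10 mm above already) | 5.4 cm | 6.00 cm |

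The RECIST column is the larger of 1.2 × entry size and entry size + 0.5 cm, for a single target lesion; the 20% condition governs at all four sizes. Every entry size above 4 cm meets 2.4.2.3 with no growth. At 3.9 cm the rules also disagree: growth of 2 mm would be progression under 2.4.2.3, but neither single-scan tumour growth nor RECIST progressive disease.

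**2. Effect on PFS.** If k of 16 patients enter above 4 cm and are counted at day 0, Kaplan-Meier PFS starts at 1 − k/16:

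- k = 0: 100%
- k = 1: 15/16 = 93.8%
- k = 2: 14/16 = 87.5%
- k = 4: 12/16 = 75.0%

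If the status is first scored at follow-up imaging, which section 5.4 schedules every six months, the same drop appears at the first scan for those tumours still above 4 cm.

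**3. Is k = 0 likely?** If a share s of entrants is above 4 cm, the chance of at least one in 16 is 1 − (1 − s)^16. For s = 5%, 10%, 20% and 30% (assumptions) this is 56%, 81%, 97% and 99.7%; the expected numbers are 0.8, 1.6, 3.2 and 4.8.

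**4. Route to the endpoint.** Section 2.2.8 points to section 2.4 for the event, and 2.4.2.3 is the only definition of progression there. The PFS link is therefore explicit. The TTP link is not, because section 2.2.7 cites nothing.

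**The case against.** The best defence is that progression implies change, so a reader would apply 2.4.2.3 as a rise from baseline stage. That may be what was meant, but the wording covers any stage above T1a, and 5.5.4.1 gives a bare size. Section 6.1.6 defines PFS without pointing to section 2.4, so RECIST progressive disease could be argued to apply; section 2.2.8 says otherwise, which leaves two readings rather than a resolution.

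It is also fair that a stage threshold always needs different growth at different entry sizes. The disagreement at 3.9 cm is therefore secondary to the conflict above 4 cm.

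Several stronger readings are tempting but not supported:

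- **Automatic removal from study.** Section 5.5 says subjects can or may be withdrawn and permits follow-up after progression. Section 4.12 is mandatory only for therapy, and also asks for follow-up per protocol.
- **A flawed primary endpoint.** Its size criterion is relative to the pre-treatment scan and is untouched. Any loss of one-year data would be indirect.
- **An inflated stopping rule.** Section 7.4 refers to tumour progression or growth in more than 50% of enrolled patients, but neither defines progression nor cites 2.4.2.3. That entrants above 4 cm count towards it is inference.
- **TTP certainly affected.** This holds only if TTP uses the section 2.4 definition.
- **The 5 cm limit is the error.** Section 1.3 describes "patients with biopsy proven primary RCC that are candidates for active surveillance (AS") and cites guideline sizes of under 3 cm and under 4 cm. Those are background, not eligibility limits, and do not show which figure should give way.

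**Conclusion.** The contradiction is explicit, and no other section resolves it: an eligible tumour above 4 cm meets the progression definition at baseline and is a PFS event under section 2.2.8 without any growth.

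The size depends on a share that the protocol does not give. Across 0 to 4 of 16 patients, PFS starts between 100% and 75.0%, or drops to that level at the first scan if scoring waits until then, no other event or censoring has occurred, and the tumours remain above 4 cm. If nobody enters above 4 cm, only the smaller inconsistency just below the limit remains.

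This should be fixed, but it is not critical. PFS and TTP are secondary estimates with no power calculation attached, and the primary endpoint keeps its own baseline-relative size rule.

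**What to change.** For both TTP and PFS, define progression relative to each patient's own baseline or nadir: the RECIST progressive disease rule already in section 6.1.4.1, plus new regional or distant disease. Delete the size above 4 cm as a stand-alone event in 2.4.2.3, and make 2.2.7, 2.2.8 and 6.1.6 cite this one definition. If a stage increase is kept as an event, count it only from the patient's baseline stage and state that it remains dependent on entry size: a 3.9 cm tumour would still change stage after just over 1 mm of growth.

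For tumours of 4 to 5 cm, sections 3.1.2, 4.12, 5.3 and 5.5.4 contradict each other and must be reconciled by the clinical team. No size limit or removal rule is proposed here.

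The cost is amendment wording; baseline tumour size is already collected (section 5.4). The downside is that some events now defined by crossing 4 cm will be recorded later or not at all. Because the RECIST rule needs more growth than the 4 mm rule at the sizes tabulated, a patient could be a local failure and still progression-free, which the protocol should state.
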